Participants will be called on their quit date to verify they are quitting on that day (and to collect outcome data). If a participant states that they are not quitting on the scheduled 'quit date', they will be given one chance to reset their quit date within the next seven days, with this date becoming their new 'quit date' (which will trigger the scheduling of all subsequent follow-up calls). For participants who are unable to be contacted at quit date, their 'quit date' will be set in the system as six days after they received their courier pack (which will trigger the scheduling of all subsequent follow-up calls). Participants will be advised to continue with their allocated treatment irrespective of any lapses back to smoking.

Outcome assessments will be undertaken at one, three, and six months after the Quit date, and at 12 months in a subsample. At the six-month follow-up, in-person carbon monoxide tests will be performed for participants who live in the Auckland region to verify self-reported continuous smoking abstinence.

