4.2. Secondary outcomes

The following secondary outcome measures will be collected over the phone on the quit date and at one, three, six and 12 months post-quit date:

- **Continuous abstinence** rates (using Russell standard) defined as self-report of smoking not more than five cigarettes in total from quit date (not collected at quit date)

Note if previous follow-up forms state they smoke more than 5 cigarettes since Quit date then subsequent follow-ups will be set to Not quit. Also, if a follow-up form is missing but the subsequent follow-up form(s) says they have smoked less than 5 cigarettes since Quit date (and no other previous follow-up forms have said they smoke more than 5 cigarettes since Quit date), then the missing follow-up form will have continuous abstinence set to 'Quit'.

- **Seven-day self-reported point prevalence abstinence** rates defined as no cigarettes, not even a single puff in the last seven days (not collected at quit date)
- **Change in average number of cigarettes smoked per day (CPD)** for participants still smoking
- **Proportion of participants who have significantly reduced smoking level** defined as reducing consumption by at least 25% (in terms of numbers of cigarettes per day)
- **Time to first lapse** (six and 12 months) defined as time to first cigarette smoked (even a single puff). From first follow-up form with question "Have you smoked any cigarettes at all in the last seven days, even a single puff?" equal to "Yes". Duration is calculated as the days since actual quit day to date of first lapse in the follow-up form.

Participants that withdraw will be censored on the last available visit, and participants that have not lapsed by the six (or 12) month follow-up will be censored on the six (or 12) months visit date. Note the first follow-up form with a lapse date will be taken since this will be more accurately remembered by participants than later visits.

- **Time to first relapse** defined as time to smoking more than five cigarettes a day for three or more days in a row. From first follow-up form with question “Have you smoked more than 5 cigarettes per day for 3 or more days in a row?” equal to “Yes”. Duration is calculated as the days since actual quit day to date of first relapse in the follow-up form

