7.5. Primary outcome analysis

The proportion of participants that have been biochemically verified as continuously abstinent at six months by group will be analysed using log-binomial regression, and the risk in each group, relative risks, absolute risk differences, and corresponding 95% confidence intervals will be calculated. All analyses for the

primary outcome will be ITT (unless otherwise stated) and include all randomised participants. Missing outcomes will be imputed using multiple imputation assuming the data is missing at random. Multiple imputed datasets will be created (n=50) and the imputation model will include baseline age, sex, and group, and the fully conditional specification logistic regression method will be used to impute the missing outcomes. The imputed datasets will be analysed using log-binomial regression and combined to output one inference. Adjusted analyses for potential covariates will be conducted if needed.

To check the robustness of the primary outcome the following sensitivity analyses will be conducted:

- self-reported continuous abstinence at 6 months (not biochemically verified)
- using the following varying cut-offs used for CO measurements: ≤ 3 ppm, ≤ 5 ppm, ≤ 8 ppm

The following sensitivity analyses will also be conducted for the primary outcome where groups will be compared using chi-squared tests:

- complete case analysis
- per protocol analyses where participants that have any major protocol violations will be excluded (see 6.2)
- assuming all missing outcomes are still smoking instead of using multiple imputation

Tests for heterogeneity will be used to examine if there is any difference in the groups on the unadjusted primary outcome for the following subgroups: baseline age (will be dichotomised based on the median), sex, ethnicity (Māori, non-Māori), education (< 12 years of attending school, 12 or more years of attending school), type of cigarettes smoked (RYO, factory made, both), AUDIT-C (low, high), cannabis use, motivation to quit, level of cigarette dependence (using HSI), and level of behavioural support received (will be categorised based on the data). Subgroup analyses will also be conducted by batch number of product received (Batch 1: early 2022, Batch 2: early 2023) to assess if there were any differences by batch.

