7.6. Secondary outcomes analysis

Descriptive summary statistics for each follow-up visit and group will be presented for all secondary outcomes. For all secondary outcomes (unless otherwise stated) participants with missing outcome data will be excluded from the analyses.

Incidence rates, risk difference, relative risks and 95% confidence intervals will be calculated for self-reported continuous abstinence (not biochemically verified), seven-day point prevalence abstinence and reduced CPD consumption by at least 50% outcomes at each follow-up visit. Both complete case analysis and ITT analysis (where missing outcomes will be imputed using the same multiple imputation method described above for the primary outcome) will be conducted.

MPSS at 3 months (for 6-month continuous abstainers only) will be analysed using linear regression and include baseline MPSS in the model. The change from baseline in each of the repeated continuous outcomes (average number of cigarettes smoked each day for smokers, weight and BMI) will be analysed using mixed models. Each model will include group and the baseline measure. The appropriate covariance structure to be used will be assessed by the likelihood ratio test. The method of maximum likelihood will be employed to ensure patients with missing data are included in the model assuming the data is missing at random. However, if all follow-up data is missing then the participant will be excluded from the analyses. Intervention by visit interaction effects will be tested. Note the

distribution of these continuous outcomes will be first assessed for normality and skewed data will be subjected to an appropriate transformation before analysis. Non-parametric analysis (Mann-Whitney tests) will be used for the continuous outcomes if data is skewed and cannot be transformed to be normally distributed.

The time to first lapse and relapse outcomes will be analysed using Kaplan-Meier curves, the log rank test, and Cox proportional hazards regression analysis.

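### Read literally, the fill-in rules for self-reported continuous abstinence complete missing forms selectively by outcome, and the imputation model cannot undo this; six-month rates come out too low if missingness is unrelated to outcome

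*SAP*

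**What the plan says.** SAP section 4.2 gives two rules for self-reported continuous abstinence.

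- **Carry forward.** "Note if previous follow-up forms state they smoke more than 5 cigarettes since Quit date then subsequent follow-ups will be set to Not quit".
- **Carry back.** If a form is missing, a later form reports abstinence and no earlier form reports more than five cigarettes, "then the missing follow-up form will have continuous abstinence set to 'Quit".

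Two design facts decide what these rules can do. The outcome is first asked at one month, since section 4.2 excludes the quit-date call. Section 2 schedules the last assessment "and at 12 months in a subsample".

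Section 7.6 analyses the outcome at each follow-up visit: "Both complete case analysis and ITT analysis (where missing outcomes will be imputed using the same multiple imputation method" as for the primary outcome. Section 7.5 specifies that method as fully conditional logistic imputation with baseline age, sex and group, assuming data missing at random. Section 7.5 also lists six-month self-reported continuous abstinence, without biochemical verification, as a sensitivity analysis of the primary outcome.

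**The concern.** Each fill is logically sound for the person concerned, provided the reports are true. The difficulty lies in who remains missing.

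No earlier form can mark a missing one-month form as a failure, so it is either filled as Quit or stays missing. A missing six-month form can be filled as Quit only from a 12-month form, which most participants may not have, so it is filled almost only as Not quit. Those left missing at six months are therefore mainly people last seen abstinent or never seen to fail.

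Complete-case analysis drops this remainder. The imputation draws values for it from participants of the same age, sex and group, a pool that now contains the carried-forward failures. Neither analysis uses the person's own status at other visits. What is at stake is the abstinence rates and risk differences for an important secondary outcome, and the usefulness of the self-report result as a robustness check on the primary outcome.

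**Working it through.** The SAP gives no figure for this effect, so there is none to reproduce. Its only relevant inputs (section 2.4) are six-month verified rates of 25% (combination), 12% (cytisine) and 9% (e-cigarette), and 28% loss at six months. The rest is assumed.

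**Assumed illustration.** True continuous abstinence at 1, 3 and 6 months is 45/35/27% (combination) and 30/20/14% (cytisine). Missingness is 15/22/28%, unrelated to outcome. Twelve-month forms are ignored at first.

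**Six months, missingness independent across visits.** A missing six-month form stays unfilled if no returned earlier form shows failure. The unfilled share of missing forms is: abstinent at month 3, plus failed between months 1 and 3 with the month-3 form missing, plus failed by month 1 with both earlier forms missing.

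- Combination: 0.35 + 0.10×0.22 + 0.55×0.15×0.22 = 0.390. Estimate: 0.72×0.27 / (1 − 0.28×0.390) = 21.8%.
- Cytisine: 0.20 + 0.10×0.22 + 0.70×0.15×0.22 = 0.245. Estimate: 0.72×0.14 / (1 − 0.28×0.245) = 10.8%.
- Risk difference 11.0 points (true 13.0); relative risk 2.02 (true 1.93).
- True abstinence among those left unfilled: 0.27/0.390 = 69% and 0.14/0.245 = 57%. The planned model would impute them near 22% and 11%.

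**Six months, monotone dropout.** Of the 28% lost, 6% were last seen at month 3 and 7% at month 1.

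- Combination: 0.1944 / (0.72 + 0.06×0.65 + 0.07×0.55) = 24.4%.
- Cytisine: 0.1008 / (0.72 + 0.06×0.80 + 0.07×0.70) = 12.3%.
- Risk difference about 12 points.

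**One month, independent missingness.** The share of missing forms filled as Quit is 0.27×(1 − 0.22×0.28) + 0.08×0.78 = 0.316 (combination) and 0.14×(1 − 0.22×0.28) + 0.06×0.78 = 0.178 (cytisine).

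- Combination: (0.85×0.45 + 0.15×0.316) / (0.85 + 0.15×0.316) = 47.9%, against 45%.
- Cytisine: (0.85×0.30 + 0.15×0.178) / (0.85 + 0.15×0.178) = 32.1%, against 30%.
- Under monotone dropout the carry-back rule never operates and month 1 is unbiased.

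**Three months, independent missingness.** The two rules nearly cancel.

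- Combination: (0.78×0.35 + 0.22×0.72×0.27) / (0.78 + 0.22×(0.72×0.27 + 0.85×0.55)) = 34.1%, against 35%.
- Cytisine: (0.78×0.20 + 0.22×0.72×0.14) / (0.78 + 0.22×(0.72×0.14 + 0.85×0.70)) = 19.1%, against 20%.
- The risk difference stays at 15.0 points.

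**Does the imputation repair it?** A simulation used the SAP's six-month rates, assumed one- and three-month rates of 2.0 and 1.4 times those, the same independent missingness, and imputation on age, sex and group. Six-month results (combination / cytisine / e-cigarette):

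| | Estimate |
|---|---|
| True | 0.250 / 0.119 / 0.092 |
| Filled, complete case | 0.203 / 0.091 / 0.070 |
| Filled, planned imputation | 0.203 / 0.091 / 0.070 |
| Visits modelled jointly, once failed always failed | 0.250 / 0.119 / 0.092 |

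Twelve-month forms for 30% or 100% of participants raise the combination estimate from 0.203 to 0.214 or 0.237, still below 0.250.

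**The case against.** **The direction is not fixed.** A reader might infer that the rules always raise one-month and lower six-month abstinence, and distort every visit. The SAP does not support that. The one-month bias needs intermittent missingness, and month 3 is nearly unaffected. The six-month error also depends on missingness being unrelated to outcome. If smokers have twice the odds of being missing, a true 27% becomes 24.2% with independent missingness and 27.6% with monotone loss. The missing-equals-smoking sensitivity analysis in section 7.5 shows that the plan considers such loss possible. This objection stands and limits the claim.

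**The fills are true, so they should be used.** This also stands. It is tempting to conclude that the rules should never complete a case at a missing visit. But in the same scenario (odds ratio 2), a complete-case analysis without the fills gives about 30.5% against a true 27%, worse than with them.

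**The carry-forward rule may not cover missing forms.** Its sentence, unlike the carry-back sentence, does not mention missing forms. It may be meant only for returned forms that contradict an earlier report, in which case the six-month downward bias does not arise. The text, "then subsequent follow-ups will be set to Not quit", does not settle this.

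**The comparison is little affected.** Relative risks move only slightly and the risk difference shrinks, which is conservative. Nor can one infer that the primary estimate is biased by these rules: they appear under secondary outcomes, and section 4.1 does not state them for the verified outcome.

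**Conclusion.** The point holds in a conditional form. On a literal reading of section 4.2, and with missingness unrelated to outcome, both planned analyses understate six-month self-reported continuous abstinence. In the illustration, 27% v 14% becomes between 21.8% v 10.8% (independent missingness) and 24.4% v 12.3% (monotone dropout). The risk difference loses about one to two points.

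Independent missingness gave the largest error of the patterns tried. The size rests on one- and three-month rates and missingness that the SAP does not give. It would be smaller with wide 12-month coverage and could vanish or reverse if smokers are lost more often. Any such offset would be accidental and outside the missing-at-random assumption the plan adopts. The point should be corrected because the imputation omits the most informative data available, not because the trial's main conclusion is in danger.

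**What to change.** - For the imputed analysis of self-reported continuous abstinence, including the six-month sensitivity analysis of the primary outcome, add continuous-abstinence status at the other visits to the imputation model. Keep the fill rules as logical constraints, so that once a participant has failed, every later visit is a failure.
- State in section 4.2 whether the carry-forward rule applies to missing forms or only to returned forms that conflict.
- Treat the complete-case result as secondary and report it with and without the fills.

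The cost is a few sentences in the SAP and a slightly larger imputation model, using data already collected.

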Participants that withdraw will be censored on the last available visit, and participants that have not relapsed by the six (or 12) month follow-up will be censored on the six (or 12) months visit date. Note the first follow-up form with a relapse date will be taken since this will be more accurately remembered by participants than later visits.

- **Use of other medication and other methods of cessation** (participants will be asked about their use of other methods of cessation, such as NRT, Zyban, clonidine, nortriptyline, e-cigarettes, acupuncture etc)
- **Health-related quality of life** (three, six and 12 months) measured using the New Zealand EQ-5D
- **Treatment use and compliance** (quit date, one and three months): use of the allocated product. This will include daily use (and reasons for not using daily), and number of pills or pods remaining.

For participants allocated to cytisine, compliance is defined as having taken $\geq 80\%$ of the required number of tablets over the three-month intervention period.

- **Signs and symptoms of nicotine withdrawal, and urge to smoke** (three months): measured using the MPSS
- **Crossover** where participants in the cytisine-only group will be asked whether they accessed and used an e-cigarette (with or without nicotine) during the six (or 12) month study period, and participants in the e-cigarette group will be asked whether they accessed and used cytisine during the trial.
- **Change in e-cigarette use**: Participants allocated to the e-cigarette groups will be asked whether they changed the type of e-cigarette device and/or the nicotine strength and/or flavor they used in the e-cigarettes provided. If they did, they will be asked when they did this, and what the device type, nicotine strength and/or flavor was.
- **Dual use** (not collected at quit date): defined as daily use of both their allocated treatment and continued smoking of cigarettes every day.
- **Continuation of product use** (at six and 12 months in a subsample) defined as continued use of their allocated treatment after the end of the designed three-month treatment period.
- **Acceptability of the product** (three months): Participants will be asked for their views on the use of their allocated product as a cessation aid
- **Recommendations** (three months): Participants will be asked whether they would recommend their allocated treatment to another smoker who wanted to quit.

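### Time to first lapse is defined from the first puff but triggered only by a seven-day question, so a lapse that ended over a week before the next call, with no later Yes, is censored as no lapse

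*SAP*

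**What the plan says.** SAP section 4.2 gives the outcome as "defined as time to first cigarette smoked (even a single puff", counted in days from the actual quit day. The event comes from the first follow-up form with a Yes to "Have you smoked any cigarettes at all in the last seven days, even a single puff", and the event time runs to the date of first lapse on the form. For everyone else who stays in the study, "participants that have not lapsed by the six (or 12) month follow-up will be censored on the six (or 12) months visit date".

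The same look-back defines another outcome in that section, seven-day point prevalence: "no cigarettes, not even a single puff in the last seven days".

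Two neighbouring outcomes are not limited to a week. Continuous abstinence is counted from quit date, and a participant is set to not quit at later visits "if previous follow-up forms state they smoke more than 5 cigarettes since Quit date". The relapse question is quoted without any look-back: "Have you smoked more than 5 cigarettes per day for 3 or more days in a row".

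A note on which form supplies the date reads "Note the first follow-up form with a lapse date will be taken since this will be more accurately remembered".

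Section 2 places the outcome calls at one, three and six months after quit date, and at 12 months in a subsample. Section 7.6 analyses lapse by Kaplan-Meier curves, the log rank test and Cox regression.

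**The concern.** The definition covers every day since quit day, but the trigger covers only the week before each call. Someone who smoked for some days between calls, stopped, and was abstinent in the week before that call and every later one has lapsed under the definition and is censored under the derivation rule. A missed lapse followed by a Yes at a later call does become an event, but possibly with too late a date.

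Two things are at stake. The Kaplan-Meier curve would show too many people as never having smoked. One participant could also be coded as not quit on the more-than-five-cigarettes item while censored as lapse-free, which is a contradiction between two secondary outcomes in the same report. The primary outcome does not use the seven-day item.

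**Working it through.** The SAP states no figure for lapse, so there is none to reproduce. The check has three parts.

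**1. The rules side by side (SAP 4.2)**

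| Outcome | Period asked about |
|---|---|
| Continuous abstinence | since quit date |
| Time to first relapse | no look-back in the quoted question |
| Seven-day point prevalence | last seven days |
| Time to first lapse | defined since quit day; triggered by last seven days |

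Only lapse has a definition and a trigger that cover different periods.

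**2. Share of follow-up inside a window** (schedule from SAP section 2; month = 365/12 days)

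- To six months: 3 calls × 7 = 21 days; 21/182.5 = 11.5%.
- To 12 months (subsample): 4 × 7 = 28 days; 28/365 = 7.7%.
- Uncovered stretches before the four windows: about 23, 54, 84 and 176 days.

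These are shares of days, not of lapsers missed. Smoking that runs into a window gives a Yes, and the form's first-lapse date can then be earlier than the window.

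**3. Illustration of the share missed by six months**

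Inputs:
- Share never smoking by day 182, p: 25% (combination), 12% (cytisine) and 9% (e-cigarette), borrowed from the predicted quit rates in SAP 2.4. The anchor is imperfect, because that outcome allows up to five cigarettes and needs CO verification.
- Call windows: days 24–30, 85–91 and 176–182.
- Daily lapse hazard h = 1 − p^(1/182): 0.76%, 1.16% and 1.31%.
- Daily recovery r: assumed, since the SAP gives none. People who recover lapse again at the same hazard h, also assumed.

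Method: step a two-state chain (not smoking, smoking) through 182 days. Anyone smoking on a window day counts as recorded. With true lapse = 1 − p, the share of lapsers missed = 1 − recorded/(1 − p).

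| r per day | Arm (p) | True lapse | Recorded lapse | Lapsers missed |
|---|---|---|---|---|
| 0.5% | 25% | 75% | 69.1% | 7.8% |
| 0.5% | 12% | 88% | 83.0% | 5.7% |
| 0.5% | 9% | 91% | 86.5% | 5.0% |
| 1% | 25% | 75% | 64.0% | 14.7% |
| 1% | 12% | 88% | 78.3% | 11.0% |
| 1% | 9% | 91% | 82.1% | 9.8% |

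Missed shares were computed before rounding. Example: 1 − 64.0/75 = 14.7%. If people who recover never smoke again, the same settings give about 12% to 23% missed, so the result depends on the re-lapse assumption too.

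Cox hazard ratio, combination v cytisine, with every recorded event given its true first-lapse date: true value 0.655. With equal recovery of 0.5% or 1% a day in both arms it is 0.656 or 0.657. With recovery of 2% v 1% it is 0.541, and with 1% v 2% it is 0.797. The unequal rates are invented to show that bias can go either way.

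**The case against.** The strongest reply is that the forms evidently hold a lapse date separate from the seven-day tick, and that the note about the first form with such a date makes it the real source. If the date was asked whatever the tick, the data exist and the defect is one loosely worded sentence. That possibility stands. But the note gives recall as its reason, so it chooses between forms, and it recurs for relapse ("Note the first follow-up form with a relapse date will be taken since this will be more accurately remembered"), where there is no seven-day limit to override. It does not clearly displace the stated trigger. If both were meant, the SAP has two triggers that can disagree and does not say which governs.

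Three stronger readings are tempting and are not supported:

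- *Every lapse between calls is lost.* No. Smoking that reaches a window is caught, and a later Yes makes the participant an event.
- *A participant can have a relapse but no lapse.* This requires the relapse question to be asked whatever the seven-day answer. The form is not shown, and SAP section 3 shows that the baseline questionnaire uses skips. The point carries no weight here.
- *The treatment comparison is biased, or a third or more of lapsers are missed.* With equal recovery the hazard ratio hardly moves, and nothing in the SAP suggests that recovery differs by arm. Missed shares that large need faster recovery or no re-lapse, and the SAP supports neither assumption.

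It is also fair to say that a full reconstruction, with midpoint dating and sensitivity checks, would be out of proportion to a secondary outcome.

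**Conclusion.** The concern holds in this limited form. Followed as written, the derivation censors some true lapsers as never lapsed, may date others late, and can contradict the coding of continuous abstinence. The Kaplan-Meier lapse curve would be too low.

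The direction follows from the text. The size cannot be estimated from the SAP, and 5% to 15% of true lapsers missed is an illustration. It rests on the borrowed never-smoking shares, a constant lapse hazard, the assumed recovery rates and equal re-lapse. The arm comparison is at risk only if recovery from lapses differs by arm, and the document gives no direction for that.

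Severity is minor: one secondary outcome is affected.

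**What to change.** In SAP 4.2, keep the seven-day item for point prevalence only. For time to first lapse:

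1. Take the event from the first form with a recorded first-lapse date, whatever the seven-day answer, and use that date.
2. Count a participant who reports more than five cigarettes since quit date, or a relapse, as having lapsed no later than that form, or no later than the relapse date if one is given.
3. If lapse dates were collected only after a seven-day Yes, relabel the outcome *first lapse detected at a follow-up call* and state that lapses between calls can be missed.

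Cost: a few lines of SAP text and a little derivation code, using items the SAP already names. No new data or model is needed. The downside is that some events will be imprecisely dated, and lapses of one to five cigarettes between calls may stay unrecorded if the form did not ask about them. Settling the rule before data lock also removes a choice between two readings once results are visible.
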